- c. Plasma biomarker analyses. Prostaglandin metabolites (PGE2 and 6-keto-PGF1-alpha), matrix metalloproteinases MMP2 and MMP9, cathepsin K, and a cytokine array will be measured on serial plasma samples (weeks 0, 8, 16, 24) from subjects on this trial. Marked changes in these metabolites are expected when subjects are on celecoxib, and this will serve as a potential biomarker of drug effect and compliance.
- d. Exhaled breath condensates (EBCs). EBCs will be obtained from subjects on this trial at the time of pulmonary function testing (week 0, 24). Subjects will be required to withhold food and carbonated beverages for one hour prior to EBC collection. An Rtube (Respiratory Research, Austin, TX) will be used to collect EBCs by tidal breathing through the mouth for 10 minutes without a nose clip. The metal sleeve surrounding the collection chamber will be chilled to -20°C for at least one hour prior to EBC collection. The EBC will then be stored at -80°C under N2 gas to prevent non-enzymatic oxidation of the parent fatty acids and lipid mediators. Samples will be analyzed for prostaglandin metabolites (PGE2 and 6-keto-PGF1-alpha).
- e. Plasma cell-free DNA (cfDNA) will be isolated from each subject on this trial at each time point a sample is drawn. The plasma will be separated, and cfDNA isolated. The cfDNA will be subject to targeted next generation sequencing to search for mutations in TSC2.

VI- Biostatistical analysis

b- Data variables

We will collect information about the safety of Celecoxib in women with LAM and TSC. In particular, we will collect data on the incidence of adverse events and severe adverse events. In addition, we will collect information about lung function at the screening visit and at the end of the study period. If subject has a renal angiomyolipoma at the screening visit, we will collect information about angiomyolipoma size at the end of the 6 months of therapy.

c- Statistical Methods

Sample Size Considerations

Common adverse event rate with Celecoxib provided in the package insert are between 0.2% and 6.0%. The below table gives the probability of seeing at least one case of common adverse event associated with Celecoxib, using different event rates (Table 2).

Table 2. Probability of observing at least one case of an adverse event

	Adverse event rate		
Sample size	6%	2.5%	0.2%
12	52%	26%	2.3%

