With the proposed sample size of 12 subjects will allow us to detect at least one case of common adverse event with probability of 2.3% to 52%. Rates of side effects related to celecoxib in the LAM population are unknown.

For lung function parameters (FEV1, FVC, DLCO) and angiomyolipoma size (when applicable), the difference between baseline and 24 weeks of therapy will be assessed using the Wilcoxon signed-rank test, with a two sided alpha at 0.05.

For the exploratory endpoints, difference between baseline and 24 weeks of therapy will be assessed using parametric and non-parametric tests as indicated. Two-sided alpha of 0.05 will be used to determine statistical significance.

VII- Risks and Discomforts

a- Risks of Celecoxib

Cardiovascular Risk

Celecoxib may cause an increased risk of serious cardiovascular thrombotic events, myocardial infarction and stroke which can be fatal. All NSAIDs may have similar risk. This risk may increase with duration of use. Patients with cardiovascular disease or risk factors for cardiovascular disease may be at greater risk. The cumulative risk is 2.5% over 3 years at the Celecoxib dose that we are using in this study.

Hypertension

Celecoxib can lead to new onset hypertension or worsening of existing hypertension. The rate of hypertension in one trial was 2.4%

Gastrointestinal Risk

Celecoxib cause an increased risk of serious gastrointestinal adverse events including bleeding, ulceration, and perforation of the stomach or intestines, which can be fatal. These events can occur at any time during use and without warning symptoms. Elderly patients are at greater risk for serious gastrointestinal events. The incidence after 9 months of therapy of complicated and symptomatic ulcers was 0.78% in one study, but the risk was 1.4% in patients older than the age of 65. Concomitant use of aspirin increased the risk to 3.06%.

Hepatic Risk

The incidence of borderline elevation (greater than 1.2 times and less than 3 times the upper limit of normal) of liver enzymes was 6% in one trial. The incidence of significant elevation in liver enzymes was 0.2%

Renal Risk

Renal toxicity can be seen especially in patients with pre-existing impairment of kidney function, heart failure or liver disease taking diuretics. No percentage on the occurrence of renal toxicity with Celecoxib is provided in the package insert.

Skin reactions

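### Do the unlabelled rates in Table 2, and the lack of a stated interval for adverse-event proportions, leave the safety objective of this 12-subject pilot unsupported?

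*Combined protocol and SAP*

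**What the plan says.** Section II makes the safety and tolerability of celecoxib in LAM the main objective, together with a pilot look at benefit, as a step towards phase II/III studies. Section III-a sets enrolment at up to 12 women over two sites. The Stopping rules text in Section V gives 24 weeks of follow-up on therapy.

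Section VI-c opens its sample-size paragraph with "Common adverse event rate with Celecoxib provided in the package insert are between 0.2% and 6.0" per cent. Table 2 then "gives the probability of seeing at least one case of common adverse event associated with Celecoxib, using different event rates": for 12 subjects, 52% at a 6% rate, 26% at 2.5% and 2.3% at 0.2%. The text adds that this sample size "will allow us to detect at least one case of common adverse event with probability of 2.3% to 52" per cent, and that "Rates of side effects related to celecoxib in the LAM population are unknown".

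On the handling of safety data, Section VI-b says "In particular, we will collect data on the incidence of adverse events and severe adverse events". Section V (Primary outcome measurements) places every subject with at least one dose in the side-effect analysis and grades toxicity by CTCAE. The only named test in VI-c is for lung function and angiomyolipoma size, where "the difference between baseline and 24 weeks of therapy will be assessed using the Wilcoxon signed-rank test".

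Section VII-a lists rates on different time bases. On cardiovascular events it says "The cumulative risk is 2.5% over 3 years at the Celecoxib dose that we are using in this study", having noted that "This risk may increase with duration of use". Ulcers are 0.78% after 9 months. Hypertension is 2.4%, and liver-enzyme elevations are 6% (borderline) and 0.2% (significant), all without a period.

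**The concern.** A probability of seeing an event within 24 weeks has meaning only if the rate put into it is a 24-week rate, and Table 2 does not say that its rates are. All three match figures in Section VII-a, and the only 2.5% there is the 3-year cardiovascular risk. If that is the source, a 3-year risk was used as a 24-week risk, and 26% overstates the chance of seeing such an event.

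The secondary measures have a test and an alpha level, while the main objective has neither an interval nor a statement of precision. At Table 2's own rates, no event of a given type is a likely result, and the plan does not say how to read it. A clean 0 of 12 could then be taken as stronger reassurance than it is when a later trial is planned.

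**Working it through.** **Inputs.** n = 12 and rates of 6%, 2.5% and 0.2% (VI-c, Table 2); enrolment of up to 12 (III-a); follow-up of 24 weeks (V); 2.5% over 3 years and 2.4% hypertension (VII-a).

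**1. Reproduce Table 2.** P(at least one) = 1 − (1 − p)^12.

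| p | Calculation | Result | Printed | P(no event) |
|---|---|---|---|---|
| 6% | 1 − 0.94^12 | 52.41% | 52% | 47.6% |
| 2.5% | 1 − 0.975^12 | 26.20% | 26% | 73.8% |
| 0.2% | 1 − 0.998^12 | 2.374% | 2.3% | 97.6% |

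All three printed values are consistent with truncation. Only the third differs from the rounded value (2.4%).

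**2. Where could 2.5% come from?** Hypertension at 2.4% gives 1 − 0.976^12 = 25.3%, which does not print as 26% by rounding or by truncation, so it is not the source. That leaves the cardiovascular figure or an illustrative middle value. The matching numbers suggest the former. Against it, VI-c speaks of common adverse events, whereas VII-a is describing serious thrombotic ones, and VI-c credits only the range 0.2% to 6.0% to the package insert. The documents do not settle the question.

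**3. What if it is the 3-year risk?** Take 3 years as 156 weeks and a cumulative hazard of −ln(0.975) × (24/156)^k. The shape k is an assumption.

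| k | P(at least one in 12 over 24 weeks) |
|---|---|
| 2 (risk rises with time) | 0.7% |
| 1 (constant hazard) | 4.6% |
| 0.5 (front-loaded) | 11.2% |
| 0.4 | 13.4% |
| 0.3 | 15.9% |

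The constant-hazard case corresponds to a 24-week risk of 0.39%. Every value shown is below 26%, but the size of the gap depends on k. The documents give no k; VII-a says only that risk may rise with duration.

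**4. What the counts will show.** For no events in n subjects, the exact 95% upper limit is 1 − 0.025^(1/n) two-sided and 1 − 0.05^(1/n) one-sided.

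| Result | Two-sided 95% | One-sided 95% upper limit |
|---|---|---|
| 0 of 12 | 0% to 26.5% | 22.1% |
| 0 of 8 | 0% to 36.9% | 31.2% |
| 1 of 12 | 0.2% to 38.5% | – |

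These limits need only the number of events and the number treated, and the plan collects both.

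**5. What depends on Table 2?** The stopping criteria in Section V are triggered by individual events (a related death or related grade IV toxicity), not by a rate. The signed-rank tests do not use the table. The small sample is also justified separately, in the text on protection against medication risk in Section VII, as fitting an exploratory trial.

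**The case for a change.** The best case for a change is that the gap falls on the main objective and costs almost nothing to close. Each Table 2 rate could be labelled with its event and period, and one sentence could promise exact intervals. Because rates in LAM are unknown, what the data can exclude is more informative than the chance of seeing one event. After 0 of 12, the two-sided interval covers all three tabulated rates, and its upper limit is 26.5/6 = 4.4 times the largest of them. Being a pilot is no answer to this, since estimation with intervals is what suits a pilot.

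The factual part stands: the labels are absent, the interval is unstated, and 0 of 12 is weak evidence. The inference to a needed change does not. Separating 6% from 0.2% is not an aim of this trial. For the two-sided upper limit after no events to fall below 6%, n must be at least ln(0.025)/ln(0.94) = 59.6, that is 60 subjects. Nor does the plan hide its limits. It prints detection probabilities as low as 2.3%, whose complements are the probabilities of no event, and it says that rates in LAM are unknown. Saying that an event may be detected with a stated probability claims nothing about precision. An exact interval is fixed once the counts and the treated set are fixed, so leaving it unstated gives the analyst no choice that could bias the result.

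**Conclusion.** The concern does not call for a change. Table 2 is arithmetically right apart from 2.37% printed as 2.3%, a clerical slip that alters no decision. The one claim that would make a printed figure materially wrong (26% against about 4.6% under a constant hazard) needs two assumptions that the documents do not supply: that 2.5% is the 3-year cardiovascular risk, and a particular hazard shape. Even if both held, enrolment, stopping and the planned tests would be unaffected.

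What is left is labelling and an unstated interval in a descriptive, single-arm pilot. The plan names incidence as its safety summary, defines the treated set and the grading, and provides independent safety-board review (IX-a). Followed as written, it yields sound adverse-event incidences. A competent report would give them with exact limits at the number actually treated: an upper limit of 26.5% for 0 of 12, or 36.9% if only 8 were treated. This conclusion rests on the study being read as its authors describe it, as exploratory, and not as proof that any given event is rare.

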Celecoxib is a COX-2 selective non-steroidal anti-inflammatory drug (NSAID). It is used to treat osteoarthritis, rheumatoid arthritis, ankylosing spondylitis, and several other inflammatory conditions. It has been in clinical use in the USA for 16 years. Celecoxib is generally well tolerated, with mild to moderate upper GI complaints being the most common adverse event (McCormack 2011). Although celecoxib has been associated with an increased risk of cardiovascular events, including myocardial infarction (MI) and stroke, this has been inconsistent in meta-analyses (McCormack 2011). Nonetheless, due to this potential risk, LAM patients with a history of MI or stroke will not be entered on this trial. Celecoxib and other NSAIDs may increase risk of serious gastrointestinal (GI) ulceration, bleeding, and perforation. To minimize this risk, LAM subjects on this protocol will not take any other NSAID, and omeprazole will be permitted for use concurrently for any LAM subjects on this trial. In addition, LAM patients with a prior history of ulcer disease or GI bleeding will be excluded from this protocol. Celecoxib and other non-steroidal anti-inflammatory drugs (NSAIDs) are known to reversibly affect renal function. For this reason, subjects with impairment of renal function will be excluded from the trial, and renal function will be monitored among subjects on this trial.

c- Rationale and hypothesis

As shown above, we have demonstrated that COX-2 and prostacyclin synthase expression is markedly increased in TSC2 deficient cells, and have also shown that prostaglandin metabolites are altered in angiomyolipoma cells. We have shown that treatment with a COX-2 inhibitor changes the PG metabolite profile of the angiomyolipoma cells, and inhibits their growth in vitro. Furthermore we have shown that COX-2 inhibition reduces growth of TSC2 deficient cells in vivo in two *Tsc* mouse models. Thus, **we hypothesize that COX-2 inhibition may be effective for TSC and LAM patients in reducing LAM and angiomyolipoma cell growth, and in stabilizing lung function.**

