We further hypothesize that COX-2 inhibition will decrease the number of circulating *TSC2*-mutant LAM cells. Previous studies from the [name] laboratory at NIH have shown that circulating LAM cells can be isolated by a combination of density gradient separation and FACS separation using antibodies to CD45 and CD235a (Crooks et al. 2004, Cai et al. 2014). We will use this same methodology followed by NGS to identify mutations in *TSC2* in patients enrolled on this study. We will then use similar methods to quantify the number of circulating LAM cells in the subjects enrolled on this trial, developing a novel biomarker of LAM. Since this method works on a blood sample, it is non-invasive.

II- Specific Aims

The main objective of **COLA: A Pilot Clinical Trial of COX-2 inhibition LAM and TSC** is to test the safety and tolerability of celecoxib in subjects with LAM, and to test in a pilot manner its potential therapeutic effectiveness. If successful, this pilot study will enable future phase II/III studies formally evaluating efficacy of this therapy for LAM. A second objective of this study is to develop a novel biomarker of LAM, the number of circulating LAM cells per ml of blood.

Specific Aims

Aim 1: To investigate whether, in LAM patients, celecoxib is safe and well tolerated, and has evidence of clinical benefit. LAM patients diagnosed by consensus criteria (Johnson et al. 2010) and with mild to moderate disease will be treated with celecoxib at 200mg PO QD. Assessments will include history and physical examination, chemistries, complete blood count, renal function assessment, and health status questionnaire during 6 months of treatment. To assess benefit, we will measure pulmonary function, angiomyolipoma size, VEGF-D levels, and quality of life using the St. George's Respiratory Questionnaire, before and after therapy with celecoxib. Twelve LAM patients at the two sites (BWH and NIH) will be enrolled on this study.

Aim 2: To investigate the potential value of novel biomarkers of LAM, quantitative measurement of the number of *TSC2* mutant LAM cells per ml of blood and/or identification of *TSC2* mutations in plasma cell-free DNA, to assess disease severity. We will develop a next gen sequencing (NGS) assay on FACS sorted circulating LAM cells and/or plasma cell-free DNA to quantitatively determine the number of *TSC2* mutant LAM cells per ml of blood and/or the amount of *TSC2* mutant DNA molecules per ml of plasma.

III- Subject selection

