a- Inclusion and exclusion criteria

We will perform a two-center phase I trial of celecoxib (COX-2 inhibitor) administered at 200mg by mouth daily for 6 months. The two centers are BWH and the National Institutes of Health Clinical Center. Up to 12 adult women with LAM will be recruited at both sites, and up to 8 subjects at BWH (between 4-8 at each site). The study will use the following eligibility criteria.

Inclusion criteria

- a. Female of age 18 to 69
- b. Ability to give informed consent
- c. Definite diagnosis of LAM

Typical cystic change on CT scan of the chest plus one of the following i) biopsy or cytology of any tissue demonstrating LAM, ii) angiomyolipoma, chylothorax, clinical or genetic diagnosis of tuberous sclerosis, iii) serum VEGF-D > 800pg/ml

- d. post-bronchodilator forced expiratory volume in one second \geq 70% of predicted and DLCO \geq 70% predicted during baseline visit.
- e. Women of childbearing potential must agree to use two forms of barrier contraception after screening visit, for the duration of study participation and for 30 days after last dose.

Exclusion criteria

- a. History of intolerance to non-steroidal anti-inflammatory drugs (NSAIDs)
- b. History of current regular use (daily most days of the week) of NSAIDs
- c. History of use of rapamycin or everolimus
- d. Uncontrolled intercurrent illness
- e. Pregnant, breast feeding or planning to become pregnant in the next 2 years
- f. Significant hematological (platelet count <100.000/ μ l or hepatic abnormalities (Liver function tests >2 times normal).
- g. Use of an investigational drug within 30 days of study start
- h. Inability to attend scheduled clinic visits
- i. Inability to give informed consent
- j. Inability to perform spirometry
- k. Creatinine > 1.0 mg/dl or eGFR < 60 ml/min
- l. Pneumothorax within past 8 weeks
- m. History of malignancy in the last 2 years other than basal cell skin cancer
- n. Use of estrogen containing medication within 30 days of enrolment
- o. Currently taking doxycycline, metformin, lupron or simvastatin

- p. Unable to undergo MRI
- q. History of seizure within the last year
- r. History of hepatitis or known active hepatitis B or C, or HIV positive serology
- s. Angiomyolipoma of diameter ≥ 4 cm
- t. History of vascular disease, including myocardial infarction or stroke
- u. History of ulcers or GI bleeding
- v. Allergy to sulfonamides, unless subject has previously used Celecoxib without any adverse reactions.

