Blood samples (chemistry, CBC) and biomarkers (VEGF-D, circulating TSC2 mutant cells) will be obtained via blood draws at indicated study visits. In addition, urine pregnancy testing will be performed at each study visit during the course of drug administration. Pulmonary function testing will be performed in accordance with ATS guidelines (Anonymous 1991) and according the schedule outlined in Table 1. Abdominal MRI will be performed at enrollment –if not done in the past 3 months-, and if angiomyolipoma or any other kidney abnormalities are detected, follow-up MRI will be performed at the discretion of the study team as indicated in Table 1. The St. Georges Respiratory Questionnaire (SGRQ) will also be administered and scored in accordance with published guidelines (Barr et al. 2000). Information on hospitalization and side effects will be obtained via direct subject interviews and medical record review.

Table 1: study visits and testing

Week

	Baseline	8	16	24
Visit number	1	2	3	4/early termination
Informed consent	X			
History and physical	X	X	X	X
Concurrent Medication Reconciliation	X	X	X	X
Adverse Event Review	X	X	X	X
Drug Administration Record	X	X	X	X
Liver, renal, glucose, cholesterol	X	X	X	X
EKG	X			
Urine pregnancy	X	X	X	X
CBC diff	X	X	X	X
MRI abdomen	X			X
Full PFT	X			X
St George's questionnaire	X			X
Stored serum and plasma	X	X	X	X
Exhaled breath condensate	X			X
measurement of TSC2 mutant cells	X			X

Study Windows

The screening to first dose period will be 28 days. All other study visit windows will be +/- one week.

Study visit procedures

Screening Visit (Visit 1)

The Screening Visit will take about 5 hours.

The following testing will be performed at the screening visit:

- Medical history
- Full physical exam
- Medication reconciliation
- Blood collection as outlined in table 1
- Urine pregnancy testing
- EKG
- MRI of the abdomen if not done in the last 3 months
- St. George's Respiratory Questionnaire (SGRQ)
- Spirometry, Post Bronchodilator spirometry, body plethysmography and diffusing capacity for carbon monoxide (DLCO)
- Stored blood for all exploratory endpoints
- Collection of exhaled breath condensates

Subjects who meet the inclusion criteria will be enrolled in the study and will start taking their medications

Visit 2

Visit 2 will take place 8 weeks after a subject starts taking study medication and will require about one hour.

The following testing will be obtained at this visit:

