We will perform assessments of clinical, functional and subject self-reported outcomes to assess potential benefit of celecoxib. Since lung function decline is a hallmark of LAM, we will perform spirometry, which will be interpreted in accordance with standard guidelines (Anonymous 1991). We will utilize the St. George's Respiratory Questionnaire (SGRQ) (Barr et al. 2000), as an assessment of the impact of treatment on dyspnea levels. Finally, we will record the incidence of hospitalization, complications from the disease, and other medical problems occurring during the study period

Stopping rules

The study will be monitored for the occurrence of a specified set of treatment related serious adverse events (TRSAE). The following two types of TRSAEs will be considered for early stopping of the study:

- Death considered to be probably or definitely related to Celecoxib

- Any grade IV toxicity considered to be probably or definitely related to Celecoxib

Subjects will be followed for 24 weeks while on therapy. During the 24 weeks of the trial, there will 4 study visits (screening visit and 3 visits while on therapy). Clinical and laboratory evaluations will be performed as outlined in Table 1.

Secondary outcome measurements

We will be performing several correlative studies as part of this protocol.

- a. VEGF-D levels. VEGF-D is well-known as a biomarker of LAM, and disease extent correlates with VEGF-D levels. Therefore we will measure VEGF-D prior to treatment and at serial time points during treatment. As this is a pilot study, formal statistical analysis is not planned.
- b. Circulating LAM cells. Circulating LAM cells may be isolated from peripheral blood of subjects on this trial, using density gradient and FACS methods. TSC2 mutations will be identified in these cells, if possible, and then the prevalence of LAM cells will be measured serially over time in subjects on this study. If no TSC2 mutation is identified, then mutations in other genes in this pathway (RHEB, MTOR) will be sought. However, we will not scan the entire genome in these analyses, but rather focus on just a few genes. We will test the number of circulating LAM cells over time to help assess whether the treatment, celecoxib, reduces the number of LAM cells.

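### Cheap improvement: the only specified lung-function analysis tests zero change, which is the hypothesised stabilisation itself; add an estimate with a 95% interval and say how it will be read

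*Combined protocol and SAP*

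**What the plan says.** **Hypothesis.** The rationale (section I-c) proposes that COX-2 inhibition may be effective "in reducing LAM and angiomyolipoma cell growth, and in stabilizing lung function".

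**Objective.** Under Specific Aims (II), the main objective "is to test the safety and tolerability of celecoxib in subjects with LAM, and to test in a pilot manner its potential therapeutic effectiveness". Success is meant to open the way to phase II/III studies. Aim 1 adds: "To assess benefit, we will measure pulmonary function, angiomyolipoma size, VEGF-D levels, and quality of life". Primary outcome measurements (V) gives the reason for testing the lungs: "Since lung function decline is a hallmark of LAM, we will perform spirometry".

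**Data.** Section III-a states: "Up to 12 adult women with LAM will be recruited at both sites", with 4 to 8 per site. There is one arm. Section VI-b says "we will collect information about lung function at the screening visit and at the end of the study period", and Table 1 accordingly marks full pulmonary function testing at baseline and week 24 only.

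**Analysis.** For FEV1, FVC, DLCO and, when applicable, angiomyolipoma size, section VI-c specifies one thing: "the difference between baseline and 24 weeks of therapy will be assessed using the Wilcoxon signed-rank test, with a two sided alpha at 0.05". It specifies no estimate of change, confidence interval, stabilisation margin or reference rate of decline. Power is not given for lung function; the sample-size argument (Table 2) concerns adverse events.

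**The concern.** If decline is the expected course and stabilisation is the hoped-for effect, the favourable result is no change. That is the null hypothesis of the signed-rank test. The test can show improvement or decline, but failing to reject does not show that change is absent or small, least of all with 12 or fewer pairs. With no control group and no pre-treatment slope, nothing else in the plan gives a non-significant result a meaning.

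The opposite reading is also open to error. A drug that halves a real decline leaves some decline, and the test may call it significant.

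What is at stake is what the pilot can pass on to a later trial. Its designers would need to know which 24-week changes remain compatible with the data, and a p-value does not tell them. The safety conclusions are not affected.

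**Working it through.** **1. The plan's own figure.** Table 2 gives the chance of at least one adverse event among 12 women, 1 − (1 − p)^12:

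| Event rate | Recomputed | Table 2 |
|---|---|---|
| 6% | 52.4% | 52% |
| 2.5% | 26.2% | 26% |
| 0.2% | 2.37% | 2.3% |

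It reproduces, apart from an immaterial rounding in the last row. It says nothing about lung function.

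**2. Inputs.** Two-sided alpha is 0.05 (VI-c). The number of pairs is 12 at most (III-a); 8 is taken as the low case, since 4 per site at two sites gives 4 + 4 = 8. The documents give no untreated decline and no SD of change. The decline d, in SDs of the paired change, is therefore an assumption, run from 0.25 to 1.0 with normally distributed changes.

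**3. Exact size of the test.** With 12 pairs there are 2^12 = 4,096 equally likely sign patterns under the null. The test rejects when the smaller rank sum is 13 or less, which 87 patterns satisfy in each tail: 2 × 87 / 4,096 = 0.0425. With 8 pairs it rejects at 3 or less: 2 × 5 / 256 = 0.0391. If the drug fully stabilises lung function, the chance of p>0.05 is therefore 1 − 0.0425 = 95.75%, and 1 − 0.0391 = 96.1% with 8 pairs.

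**4. The same result from an inert drug.** If the drug does nothing, the true change is −d. Simulated chance of p>0.05:

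| Assumed 24-week decline (SD of change) | n=12 | n=8 |
|---|---|---|
| 0 (full stabilisation) | 96% | 96% |
| 0.25 | 89% | 92% |
| 0.5 | 69% | 81% |
| 0.75 | 39% | 61% |
| 1.0 | 15% | 39% |

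A drug that halves a 1.0 SD decline leaves 0.5 SD, and the test then gives p≤0.05 in about 100 − 69 = 31% of trials at n=12.

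**5. What an interval would show.** Inverting the same test at n=12 takes the 14th smallest and 14th largest of the 12 × 13 / 2 = 78 pairwise averages, with exact coverage 95.75%. Mean half-width is about 0.66 SD at n=12, 0.71 SD at n=10 and 0.88 SD at n=8. In n=12 trials where the drug fully stabilises and p>0.05, about 70% of intervals still include a decline of 0.5 SD and about 39% include 0.75 SD.

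**6. Very few pairs.** With 5 pairs the smallest possible two-sided p is 2 / 2^5 = 0.0625, so the test cannot reject and no 95% signed-rank interval exists. This could happen for angiomyolipoma size. The background section puts renal angiomyolipoma at about 60% of women with sporadic LAM: 0.60 × 12 = 7.2, or 0.60 × 8 = 4.8, before lesions of 4 cm or more are excluded.

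**The case against.** **The plan draws no wrong inference.** A reader might infer that the sponsor will take p>0.05 as proof of stability. The documents do not say so. Stabilisation appears in the rationale as something the drug may do, not as an endpoint or success criterion. This objection stands: the point is a gap in the plan, not an error in its text.

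**Nor does the plan confine reporting to p-values.** Section VI-c says how the difference will be tested, not what will be tabulated. It would be too strong to say that results will appear only as non-significant. What can be said is that no estimate or interval is specified.

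**It is a small safety pilot.** This is true, and it is why the point is modest. But the stated objective includes a pilot test of effectiveness. For VEGF-D the protocol declines formal analysis because the study is a pilot; for lung function it chose a test at 0.05. Pilot status favours estimation over a bare test.

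**The size of the problem is assumed.** This stands. Across the range, an inert drug gives p>0.05 in anything from 89% to 15% of trials at n=12, and the documents cannot place this trial within it. The claim that the test discriminates poorly here cannot be proved from them.

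**An interval adds no power.** This stands too, since it inverts the same test. Among non-significant n=12 trials the lower limit averages −0.67 SD under full stabilisation and −1.06 SD under an inert drug with a 0.5 SD decline. The lower limit itself has a spread of about 0.30 SD, so the two cases overlap considerably. The gain is in reporting, not in telling drugs apart.

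**Conclusion.** The point holds as a cheap improvement. The hypothesised state for lung function is the null of the only specified test, so a non-significant result cannot by itself support it. This follows from the text and needs no assumption. The 96% figure at n=12 follows from the exact null distribution. The 89%, 69%, 39% and 15% figures rest on the assumed declines and on normal changes, and show what is possible, not what this trial will meet.

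The test is valid. It would be wrong to conclude that it should be dropped, that the sponsor has committed to misreading it, or that an interval would make the trial able to establish stabilisation. The case for an interval applies equally to angiomyolipoma size, which the same sentence of section VI-c covers.

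**What to change.** In section VI-c, keep the signed-rank test and add:

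> For FEV1, FVC, DLCO and (when applicable) angiomyolipoma size, the change from baseline to 24 weeks will also be reported as the Hodges-Lehmann estimate with a 95% confidence interval obtained by inverting the signed-rank test, and this interval will be the basis for interpretation. A p-value above 0.05 will not be read as stabilisation, and because there is no control group, neither a significant improvement nor a significant decline will by itself be attributed to celecoxib. Where 5 or fewer pairs are available, individual changes will be listed instead of an interval.

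**Cost.** Three sentences, with no new patients, visits or measurements.

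**Downsides.** The interval will be wide and may look uninformative. It cannot attribute stability to the drug. The Hodges-Lehmann estimate targets the pseudomedian, which equals the median only if the changes are symmetric.
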